1. GLOSSARY OF ABBREVIATIONS

Abbreviation	Description
AE	Adverse Event
AIC	Akaike's Information Criteria
ANCOVA	Analysis of Covariance
AR	Autoregressive
ATC	Anatomical Therapeutic Chemical
AUC	Area Under the Curve
BMI	Body Mass index
BP	Blood Pressure
BPH	Benign Prostatic Hyperplasia
BPM	Beats Per Minute
CI	Confidence Interval
CFB	Change from Baseline
CS	Compound Symmetry
ECDF	Empirical Cumulative Distribution Function
eCRF	Electronic Case Report Form
C ₂₄	24h Concentration
CV	Coefficient of Variation
DBL	Database Lock
DBP	Diastolic Blood Pressure
DRM	Data Review Meeting
ECG	Electrocardiogram
EQ-5D	EuroQual 5 Dimension Questionnaire
FAS	Full Analysis Set
FAS-I	Full Analysis Set for Incontinence
GPP	Good Pharmacoepidemiology Practice
HRQL	Health-Related Quality of Life
ICF	Informed Consent Form
ICH	International Conference on Harmonization
IP	Investigational Product
IxRS	Interactive Voice/Web Response System
LOCF	Last Observation Carried Forward
LF	Long Form
MAR	Missing at Random
Max	Maximum
MedDRA	Medical Dictionary for Regulatory Activities
MI	Multiple Imputation
Min	Minimum

Abbreviation	Description
MMRM	Mixed Model for Repeated Measures
MNAR	Missing Not At Random
N/A	Not Applicable
NA	Not Applicable
NVU	Night Time Voids Associated with Urgency
OAB	Overactive Bladder
OAB Dry	OAB in the absence of Incontinence
OAB Type	Investigator-Defined Baseline OAB Categorization
OAB Wet	OAB with Incontinence
OAB-d Type	eCRF Derived Baseline OAB Categorization
OAB-q	Overactive Bladder Questionnaire
PGI	Patient Global Impression
PK	Pharmacokinetic(s)
PRO	Patient Reported Outcomes
PPS	Per-Protocol Set
PPS-I	Per-Protocol Set for Incontinence
PT	Preferred Term
PVR	Post-Void Residual (Volume)
QC	Quality Control
QTc	Corrected QT Interval
REML	Restricted (or Residual) Maximum Likelihood
RVT-901	Vibegron (Urovant Code Number)
SAE	Serious Adverse Event
SAF	Safety Set
SAP	Statistical Analysis Plan
SBP	Systolic Blood Pressure
SD	Standard Deviation
SE	Standard Error
SOC	System Organ Class
SOP	Standard Operating Procedure
SUI	Stress Urinary Incontinence
TEAE	Treatment Emergent Adverse Event
TLF	Table, Listing and Figure
Urovant	Urovant Sciences GmbH
US	United States
UUI	Urge Urinary Incontinence
WHO	World Health Organization
WPAI-US	Work Productivity and Activity Impairment Questionnaire-Urinary Symptoms

2. PURPOSE

The purpose of this statistical analysis plan (SAP) is to ensure that the data listings, summary tables and figures which will be produced, and the statistical methodologies that will be used, are complete and appropriate to allow valid conclusions regarding the study objectives.

2.1. Responsibilities

██████████ will perform the statistical analyses and are responsible for the production and quality control (QC) of all tables, figures, and listings. The population pharmacokinetics (PK) analysis will be conducted independently and is out of the scope of this SAP. Only drug concentrations over time will be summarized.

2.2. Timings of Analyses

The primary analysis of efficacy and the analysis of safety and PK are planned after all patients complete the final study visit or terminate early from the study. No interim analyses will be performed and no Data Safety Monitoring Board has been set-up for this study. This SAP details these analyses and has been finalized prior to unblinding of the study.

3. STUDY OBJECTIVES

3.1. Primary Objective

To evaluate the efficacy of vibegron compared to placebo in patients with symptoms of overactive bladder (OAB), specifically the frequency of micturitions and frequency of urge urinary incontinence (UUI) episodes.

3.2. Secondary Objective

- To evaluate the overall efficacy of vibegron compared to placebo in patients with symptoms of OAB.

3.3. Safety Objectives

- To evaluate the safety and tolerability of treatment with vibegron.

3.4. Pharmacokinetic Objectives

- To characterize vibegron trough concentrations in patients with symptoms of OAB.

3.5. Exploratory Objectives

3.6. Brief Description

This is an international, Phase 3 randomized, double-blind, placebo-controlled with active control (tolterodine), parallel-group, multicenter study in men and women with OAB, to be conducted in conformance with ICH GCP. The study will assess the safety, tolerability, and efficacy of 75 mg vibegron versus placebo. Patients will be randomized 5:5:4 in a double-blind fashion to one of three treatment arms: vibegron 75 mg, placebo, or tolterodine ER 4 mg, all administered once daily for 12 weeks during the Treatment Period.

Patient participation in the study will be up to 17 weeks post randomization (including authorized windows). This study consists of a Screening Period (1 to 5 weeks), a single-blind Run-in Period (2 weeks), a randomized double-blind Treatment Period (12 weeks) and a Safety Follow-up Period (4 weeks). All patients who complete the Week 12 Visit may be offered the opportunity to enroll in a 40-week double-blind extension study RVT-901-3004 (which will be conducted under a separate protocol), until enrollment in that study is complete. Patients who do not enroll into the optional extension study will

have a Follow-up Visit approximately 28 days after the patient's last dose of Study Treatment (i.e., at Week 16 for patients who complete the Week 12 Visit, or approximately 4 weeks after withdrawal for patients who discontinue the study early). Additionally, Unscheduled Visit(s) may be arranged for patients with study-related safety concerns as needed.

3.7. Patient Selection

A full list of inclusion and exclusion criteria can be found in the RVT-901-3003 Clinical study Protocol Section 5.1.

3.8. Determination of Sample Size

Approximately 1,400 patients will be randomized in a 5:5:4 ratio to receive one of the following Study Treatments:

- Vibegron 75 mg + placebo to match tolterodine ER 4 mg;
- Placebo to match vibegron 75 mg + placebo to match tolterodine ER 4 mg; or
- Tolterodine ER 4 mg + placebo to match vibegron 75 mg.

Approximately 500 patients will be assigned to the vibegron and placebo treatment groups, and approximately 400 patients will be assigned to the tolterodine treatment group. Assuming that a total of 10% of patients will discontinue prior to Week 12 (for any reason), there will be approximately 450 evaluable patients in the vibegron and placebo treatment groups at the end of Week 12. Assuming 75% of the population will have OAB Wet, there will be approximately 337 evaluable patients in the vibegron and placebo treatment groups for the incontinence endpoints. The study has:

- Approximately 98% power to detect a true underlying between-group treatment difference in vibegron vs. placebo of 0.6 in change from baseline in micturitions at a two-sided 0.05 level assuming a variability estimate of 2.20 based on vibegron Study 008 data.
- Approximately 98% power to detect a true underlying between-group treatment difference in vibegron vs. placebo of 0.51 in change from baseline in urge urinary incontinence at a two-sided 0.05 level assuming a variability estimate of 1.68 based on vibegron Study 008 data.

Assuming that these endpoints are uncorrelated, this study has 96% power to reject both co-primary hypotheses at a two-sided 0.05 level. These alternative hypotheses are:

- **Co-Primary Alternative Hypothesis 1:** In patients with OAB, vibegron 75 mg will have a different mean change from baseline (CFB) in the average number of daily micturitions than placebo at Week 12.
- **Co-Primary Alternative Hypothesis 2:** In patients with OAB Wet, vibegron 75 mg will have a different mean CFB in the average number of daily UUI episodes than placebo at Week 12.

3.9. Treatment Assignment and Blinding

Randomization will occur centrally using an interactive voice or web response system (IxRS) using central, stratified randomization. There are three treatment arms to which patients will be randomized in a 5:5:4 ratio:

- Vibegron 75 mg + placebo to match tolterodine ER 4 mg
- Placebo to match vibegron 75 mg + placebo to match tolterodine ER 4 mg
- Tolterodine ER 4 mg + placebo to match vibegron 75 mg

Randomization will be stratified based on the investigator-determined baseline categorization of OAB, referred to as OAB Type: Wet or Dry (as defined in the protocol inclusion and exclusion criteria), and Sex (Female vs. Male).

Enrollment will be capped based on OAB Dry criteria and sex as follows:

- Up to 25% of the patients enrolled may meet OAB Dry criteria.
- Up to 15% of the patient enrolled may be male.

A double-blind/masking technique will be used: vibegron and its matching placebo and tolterodine ER and its matching placebo will be packaged identically so that treatment blind/masking is maintained. The patient, the Investigator, and Sponsor personnel or delegate(s) who are involved in the treatment or clinical evaluation of the patients will not be aware of the treatment group assignments.

At the end of the study (including the 28-day Follow-up Period), the official, final database will be frozen and unblinded after medical/scientific review has been performed, and data have been declared final and complete. The Sponsor and [REDACTED] as designated representative will be granted access to the unblinded database in order to analyze the data. A clinical study report will be prepared after all patients complete the study.

IxRS should be used for emergency unblinding treatment assignment in the event that this is required for patient safety.

In the event that unblinding has occurred, the circumstances around the unblinding (e.g., date and reason) must be documented promptly, and the Sponsor notified as soon as possible. Only the Principal Investigator or delegate and the respective patient's code should be unblinded. Other Site personnel and Sponsor personnel directly associated with the conduct of the study should not be unblinded.

3.10. Administration of Study Medication

Throughout the study, all Study Treatments will be taken by mouth once daily in the morning with 8 ounces of water. Study treatment may be taken without regard to meals.

During the Run-in Period, all patients will take placebo (1 tablet and 1 capsule) once daily for 2 weeks prior to the Baseline Visit. The Investigator will be aware that the Study Treatment during this period is placebo, however, the patient will NOT be told that the treatment administered during this period is placebo or that the patient needs to qualify to enter the randomized Treatment Period.

If a patient forgets to take Study Treatment in the morning, the missed dose should be taken as soon as possible on the same calendar day. However, if a dose is missed for an entire calendar day, the missed dose should not be taken on the following calendar day.

3.11. Study Procedures and Flowchart

This study consists of a Screening Period (1 to 5 weeks), a single-blind Run-in Period (2 weeks), a randomized double-blind Treatment Period (12 weeks) and a Safety Follow-up Period (4 weeks). The schedule of activities is given in [Table 3.11.1](#).

Table 3.11.1: Schedule of Activities

Study Period:	Screening/ Washout	Run-in	Treatment					Safety Follow-up/ Unscheduled	
Visit Number:	Visit #1	Visit #2	Visit #3	Diary Only	Visit #4	Visit #5	Visit #6	UNS #	Visit #7
Visit Name:	Screening ¹	Run-in	Baseline	Week 2	Week 4	Week 8	Week 12 or Early WD	Unsch- eduled ²⁵	Follow- up ²⁶
Study Day:	-49 to -15	-14	1	15	29	57	85 or Early WD		113 or Early WD + 28
Permitted Visit Window:		± 3 Days			± 3 Days	± 3 Days	± 3 Days		± 3 Days
Informed Consent	X								
Inclusion/Exclusion Criteria Eligibility Review	X	X	X						
Medical and Medication History	X	X	X						
Electronic Diary (eDiary) ² :									
eDiary Device:									
Device Setup/Function Check ³	X	X	X		X	X	X	X	
Device Training/Re-Training ⁴	X	X	X		X	X		X	
Dispense/Collect eDiary Device	X						X		
Patient Voiding Diary:									
Patient Voiding Diary Training/Re-Training ⁵	X	X	X		X	X		X	
Patient Completes Patient Voiding Diary ⁶	X	X		X	X	X	X		
Urine Volume Diary:									
Urine Volume Diary Training/Re-Training ⁵	X	X	X		X	X		X	
Dispense Urine Collection/Measurement Supplies	X								
Patient Completes Urine Volume Diary ⁷	X	X		X	X	X	X		
Diary and Visit Reminders									
Phone Calls / Optional SMS reminders ⁸	X	X		X	X	X	X		

Study Period:	Screening/ Washout	Run-in	Treatment					Safety Follow-up/ Unscheduled	
Visit Number:	Visit #1	Visit #2	Visit #3	Diary Only	Visit #4	Visit #5	Visit #6	UNS #	Visit #7
Visit Name:	Screening ¹	Run-in	Baseline	Week 2	Week 4	Week 8	Week 12 or Early WD	Unsch- eduled ²⁵	Follow- up ²⁶
Study Day:	-49 to -15	-14	1	15	29	57	85 or Early WD		113 or Early WD + 28
Permitted Visit Window:		± 3 Days			± 3 Days	± 3 Days	± 3 Days		± 3 Days
Patient Reported Outcomes ⁹ :									
Global Impression Items (PGI-Severity, PGI-Control, PGI-Frequency, PGI-Leakage, and PGI-Change)			X		X	X	X		
Overactive Bladder Questionnaire (OAB-q LF)			X				X		
Work Productivity and Activity Impairment Questionnaire-Urinary Symptoms (WPAI-US)			X				X		
EQ-5D			X				X		
Post-Void Residual (PVR) Volume ¹⁰		X					X		
Physical Exam ¹¹	X	X						X	X
ECG ¹²	X							X	
Vital Signs ¹³	X	X	X		X	X	X	X	X
Adverse Events ¹⁴	←=====→								
Serious Adverse Events ¹⁵	←=====→								
Concomitant Medication Review ¹⁶	←=====→								
Clinical Laboratory Assessments:									
Chemistry	X		X		X		X	X	X
Hematology	X		X		X		X	X	X
Urinalysis Dipstick ^{17,18}	X		X		X		X	X	X
Urine Pregnancy β-hCG (women) ¹⁹	X	X	X		X	X	X	X	X
IxRS Randomization to Study Treatment			X						
Dispense Study Treatment ²⁰		X	X		X	X		X	

Study Period:	Screening/ Washout	Run-in	Treatment					Safety Follow-up/ Unscheduled	
Visit Number:	Visit #1	Visit #2	Visit #3	Diary Only	Visit #4	Visit #5	Visit #6	UNS #	Visit #7
Visit Name:	Screening ¹	Run-in	Baseline	Week 2	Week 4	Week 8	Week 12 or Early WD	Unsch- eduled ²⁵	Follow- up ²⁶
Study Day:	-49 to -15	-14	1	15	29	57	85 or Early WD		113 or Early WD + 28
Permitted Visit Window:		± 3 Days			± 3 Days	± 3 Days	± 3 Days		± 3 Days
Study Treatment Return/Accountability Review ²¹			X		X	X	X		
Administer Witnessed Dose of Study Treatment ²²		X	X						
Pharmacokinetic Sampling (PK Subset Only):									
PK Sample Collection ²³					X	X	X		
Collect Date/Time of Prior Dose ²⁴					X	X	X		

Abbreviations: IxRS, interactive voice or web response system, PK, pharmacokinetic; WD, withdrawal; β-hCG, β-human chorionic gonadotropin

Table Footnotes:

Screening

1. The time between the Screening and Run-in Visits may be up to 5 weeks, to allow for washout of prior OAB medications (if needed) and completion of the Patient Voiding Diary and Urine Volume Diary.

Electronic Diary (eDiary)

2. The Electronic Diary (eDiary) for this study includes both the Patient Voiding Diary and the Urine Volume Diary, and will be implemented via an eDiary device (provisioned smartphone). A paper diary will be provided to all patients to be used as a back-up when necessary. If a back-up paper diary is used, it should be collected at each study visit.

eDiary Device

3. At Screening, site personnel will setup the eDiary Device, confirm proper functioning, and dispense the eDiary Device to the patient. At each subsequent visit during the Treatment Period, site personnel will confirm that the eDiary Device is functioning properly.

4. Specific training on device operation will be provided to the patient at Screening, with re-training provided at each subsequent visit.

Patient Voiding Diary and Urine Volume Diary

5. Specific training on completion of the Patient Voiding Diary and Urine Volume Diary will be provided to the patient at Screening, with re-training provided at each subsequent visit.

6. The Patient Voiding Diary should be completed by the patient on all of the 7 Diary Days **prior to** the Run-in Visit (days -21 to -15), Baseline Visit (days -7 to -1), Week 2 Visit (days 8 to 14), Week 4 Visit (days 22 to 28), Week 8 Visit (days 50 to 56), and Week 12 Visit (days 78 to 84). Patient will receive SMS text alerts and/or phone call reminders to complete the Diary.

7. The Urine Volume collection and Urine Volume Diary completion should be performed by the patient on one (1) of the 7 Diary Days prior to the Run-in, Baseline, and Weeks 2, 4, 8, and 12 Visits.

Diary and Visit Reminders

8. Patient will receive phone call reminders from the site to complete the Diary on approximately the first day and third day of each diary collection period (or next business day). Patient may consent to additional SMS Text reminders (where available).

Patient Reported Outcomes

9. Vital signs, followed by PRO Questionnaires will be the first procedure performed at visits that include PRO administration. Questionnaires will be administered at the site in the order listed in the Schedule of Activities.

Post Void Residual Volume

10. All efforts will be made to ensure the same device and operator are used for all PVR volume measurements for individual patients.

Physical/ECG/Vitals

11. A Complete Physical Exam will be performed at the Screening Visit and will include a digital rectal exam for all males. Focused physical examinations will be performed at the Run-in and Follow-up Visits, which will include a pelvic exam for women only as needed to confirm prolapse.

12. A single 12-lead ECG will be obtained at Screening.

13. Vital Signs includes Blood Pressure (average of three measurements taken 1-2 minutes apart after sitting for 5 minutes), Heart Rate, Temperature, Respiration Rate and Weight. Height will be measured only at Screening.

Adverse Events

14. Adverse events will be collected from the time a patient provides informed consent to participate in the study until the Follow-up Visit is completed.

15. Serious adverse events will be collected from the time a patient provides informed consent to participate in the study until the Follow-up Visit is completed.

Prior and Concomitant Medications

16. Concomitant medications will be reviewed and recorded at each study visit from the Screening through the Week 12 and at any Unscheduled Visits. Medications taken within 1 year of the Screening Visit for the treatment of OAB will also be recorded.

Labs

17. At Week 8, the Urine Dipstick will only be performed if clinically indicated (e.g., symptoms of urinary retention or urinary tract infection).

18. Urinalysis will be performed only if the urine dipstick tests positive for the presence of leukocytes, nitrites, or blood cells, and will be performed by the central lab.

19. Urine beta-human chorionic gonadotropin (β -hCG) will be tested for women of childbearing potential only.

Dosing/Drug

20. Dosing will occur every day from the Witnessed Dose on the day of the Run-in Visit through the day before the Week 12 Visit.

21. Study Treatment bottles should be returned by the patient at each visit. Clinic staff will perform accountability and review any discrepancies with the patient during the visit.

22. All patients will take their dose of Study Treatment on the day of the Run-in and Baseline Visits at the site as a witnessed dose. The date and time of Study Treatment dosing will be recorded

Pharmacokinetics Subset Only

23. PK samples for Population PK Analysis will be collected from a subset of patients (approximately 30% of enrolled patients) at selected sites. Pre-dose blood samples will be collected at Week 4, Week 8, and Week 12. PK samples should be collected during the clinic visit after all other study assessments have been completed.

24. The date and time of the last dose of Study Treatment prior to PK sampling will be recorded.

Follow-up/Unscheduled

25. Unscheduled Visits and the specific procedures performed at these visits will be determined by the Investigator, as clinically indicated. The procedures indicated in the Schedule of Activities will be performed at these visits, as clinically indicated, based on the purpose of the visit (e.g., follow-up for an adverse event or abnormal laboratory test, study treatment dispensation). The reason for the visit will be captured in the source documents.

26. For Patients who do not enroll into the optional extension study (RVT-901-3004) or patients who withdraw from the study for any reason, a Follow-up Visit should be performed approximately 28 days after the last dose of Study Treatment on Study Day 113 or approximately 28 days after a patient's Withdrawal from the study. When a patient withdraws from the study prior to study completion, all applicable activities scheduled for the Week 12 Visit should be performed at the time of withdrawal.

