Baseline will be the data collected during the Run-in Period. If greater than 10 complete diary days are available in the Run-in diary, only the complete diary days within the 10 days prior to the Baseline visit will be used; if 4 or more and less than 10 complete diary days are available, all complete diary days in the Run-in diary will be used to calculate Baseline. If less than 4 complete diary days are available, the Baseline will be regarded as missing. For a patient to have an evaluable change from baseline, the patient must have both a baseline diary and a post-baseline diary from any post-baseline timepoint, after analysis window has been applied (i.e., Week 2, Week 4, Week 8, or Week 12).

Definition of Baseline for Endpoints not Derived from the Patient Voiding Diary

Baseline value for all secondary efficacy, exploratory and safety endpoints will be defined as the last non-missing assessment before starting double-blind treatment.

Screening/Washout Period

The Screening/Washout Period covers Day -49 (Screening Visit) to Day -15 (the day before the start of the Run-in Period), which includes a 28-day washout period followed by 7-days of Diary completion. Patients not requiring the 28-day washout period can begin the 7-day Diary the day after the Screening Visit.

Run-in Period

The Run-in Period covers the duration between screening (Day -14) and the day before baseline (Day 1). There is no day 0 included in the study.

Treatment Period

The Treatment Period covers the duration that a patient is in the study from Baseline (Day 1) and Week 12.

Safety Follow-up Period

The Safety Follow-up Period continues for 28 days after the last dose of study treatment (Day 85) through Day 113 (Follow-up Visit).

Definition of Study Completion

A patient will be defined as “completed” if she/he completes the Week 12 study visit.

End of Study Definition

End of study is defined as the date when the patient has completed one of the following: completed the follow-up visit after the Week 12 visit, enrolled into the extension trial 3004, permanently discontinued from the study, or lost to follow-up. When lost to follow-up, the latest date of assessment/event in the database will be used as the last known date of the patient in study.

Day of Study Event (Post-Randomization)

Day of study event = Event Date – Date of Randomization (Day 1) + 1.

Day of Study Event (Pre-Randomization)

Day of study event = Event Date – Date of Randomization (Day 1).

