8.1.1.1. Primary Analysis

A mixed model for repeated measures (MMRM) with restricted maximum likelihood estimation will be used as the primary analysis model for change from baseline in average number of daily micturitions at Week 12. This model includes data from Week 2, Week 4, Week 8 and Week 12 and corrects for data that is missing at random (MAR), accounting for the fact that measurements taken on the same patient over time tend to be correlated, by using all available information on patients within the same covariate set to derive an

estimate of the treatment effect for a MAR-free population. No imputation of missing data is required for this analysis. The analysis model will include terms for treatment, visit, OAB Type (Wet vs Dry), Sex (Female vs Male), Region (US vs non-US), baseline score, and interaction of visit by treatment.

Primary inference will be drawn from the treatment difference between vibegron and placebo at Week 12. The comparisons between tolterodine and placebo will be reported with nominal p-values. The standard error and 95% CI for the differences will also be presented with the corresponding p-values. Additionally, estimates of least-squares means, standard errors, and 95% CIs will be presented for each treatment group (placebo, vibegron and tolterodine). The table output will also include treatment group estimates and treatment differences between vibegron and placebo, and tolterodine and placebo at Weeks 2, 4, and 8 from this model.

An unstructured covariance matrix will be used to model the correlation among repeated measurements. The Kenward-Roger adjustment will be used with restricted (or residual) maximum likelihood (REML) to make statistical inference. If the unstructured covariance model fails to converge with the default Newton-Raphson algorithm, the Fisher scoring algorithm will be used to provide initial values of the covariance parameters. In the rare event that none of the above methods yield convergence, the following structures will be investigated: heterogeneous Toeplitz, Toeplitz, heterogeneous First-Order Autoregressive [AR (1)], heterogeneous compound symmetry (HCS), and compound symmetry (CS). The covariance structure converging to the best fit, as determined by Akaike's information criterion (AIC), will be used.

An example of the SAS code for the base procedure is given below:

```
proc mixed data = datain method = reml ;
  class TRTP AVISITN USUBJID OABTYPE SEX REGION ;

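### Two voiding diaries are collected before randomisation, but the diary change models shown adjust only for the second: a cheap, modest gain in precision is left unused

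*SAP*

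**What the plan says.** **Data collected.** Footnote 6 of Table 3.11.1 (SAP 3.11) asks for a 7-day voiding diary before "the Run-in Visit (days -21 to -15), Baseline Visit (days -7 to -1), Week 2 Visit (days 8 to 14") and the later visits. Footnote 7 asks for a urine-volume collection on "one (1) of the 7 Diary Days prior to the Run-in, Baseline, and Weeks 2, 4, 8, and 12 Visits". SAP 6.3 describes the Screening/Washout Period as one "which includes a 28-day washout period followed by 7-days of Diary completion", so the first diary follows any washout of earlier overactive bladder (OAB) drugs. The second falls in the single-blind placebo run-in (3.10). Both come before randomisation at Visit 3.

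**Data used.** For diary endpoints, SAP 6.3 states: "Baseline will be the data collected during the Run-in Period". For the micturition mixed model, 8.1.1.1 states: "The analysis model will include terms for treatment, visit, OAB Type (Wet vs Dry), Sex (Female vs Male), Region (US vs non-US), baseline score", plus the visit-by-treatment interaction. The UUI model (8.1.2.1) is similar but drops OAB Type. Urgency (8.2.2), total incontinence (8.2.5) and volume voided (8.2.7) refer back to 8.1.1.1. None of the models shown has a term for the pre-Run-in diary.

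**The concern.** A diary average over 4 to 10 days measures a patient's usual level with error, and for volume voided the baseline is a single day. A second reading of the same variable, taken with the same instrument before randomisation, will usually explain some Week 12 variation that the run-in diary misses. Because it precedes treatment, adjusting for it leaves the treatment contrast valid and should narrow its standard error.

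What is at stake is precision. Both co-primary tests must succeed before any key secondary is tested, and the key secondaries are then tested in a fixed order that stops at the first failure (6.2, 8.2.1). The SAP states power only for the co-primaries.

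**Working it through.** **Inputs from SAP 3.8.** For micturitions the planned difference is "0.6 in change from baseline in micturitions at a two-sided 0.05 level", "assuming a variability estimate of 2.20 based on vibegron Study 008 data", with 450 evaluable patients per arm. For UUI it is "0.51 in change from baseline in urge urinary incontinence at a two-sided 0.05 level", with variability 1.68 and 337 evaluable per arm.

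**Step 1: the SAP's own power.** SE = SD × √(2/n), and power ≈ Φ(difference/SE − 1.96).
- Micturitions: SE = 2.20 × √(2/450) = 0.147; 0.6/0.1467 − 1.96 = 2.13; power 98.3%.
- UUI: SE = 1.68 × √(2/337) = 0.129; 0.51/0.1294 − 1.96 = 1.98; power 97.6%.
- Joint, if uncorrelated: 0.983 × 0.976 = 96.0%.

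These agree with the stated 98%, 98% and 96%.

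**Step 2: what a second diary adds.** Let r1 and r2 be the correlations of the pre-Run-in and run-in diaries with Week 12, and r12 the correlation between the two diaries. With both diaries in the model, R² = (r1² + r2² − 2·r1·r2·r12)/(1 − r12²). The ratio of residual variances, with and without the first diary, is (1 − R²)/(1 − r2²). The SAP gives none of these correlations, so all are assumed:

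| r1 | r2 | r12 | Variance ratio | Cut |
|---|---|---|---|---|
| 0.45 | 0.60 | 0.75 | 0.640/0.640 = 1.000 | 0% |
| 0.55 | 0.60 | 0.75 | 0.617/0.640 = 0.964 | 3.6% |
| 0.50 | 0.50 | 0.70 | 0.706/0.750 = 0.941 | 5.9% |
| 0.60 | 0.60 | 0.70 | 0.576/0.640 = 0.901 | 9.9% |
| 0.70 | 0.70 | 0.70 | 0.424/0.510 = 0.830 | 17.0% |

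The first row is the limiting case r1 = r2 × r12, where the first diary predicts nothing beyond the second.

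**Step 3: a second route, micturitions only.** Model each diary as a stable patient level, a slow drift (60-day decay) and independent diary noise, at days −18, −4 and 81. Set the variance of change to 2.20² and the SD of the level to 2.5 to 3.5 (assumed).
- Across all splits between drift and noise, the cut is 1.2% to 19.8%. Simulating only patients with at least 8 micturitions per day on both diaries (mean 10.5) gives 1.1% to 16.5%.
- With noise at 50% to 70% of within-patient variation and no truncation, the cut is 8% to 15%. This gives no variance to patients differing in their response over 12 weeks.
- If half of the variance of change is such differing response, the cut falls to about 6% to 8.5%. At 70% it falls to about 4% to 5.4%.

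**Step 4: effect on power.** Multiply both SDs by the square root of the variance ratio, treating 2.20 and 1.68 as residual SDs after baseline adjustment and giving UUI the same cut:
- 5% cut: 98.7% × 98.1% = 96.9%.
- 10% cut: 99.1% × 98.6% = 97.7%.
- 17% cut: 99.4% × 99.1% = 98.5%.

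The micturition SE falls from 0.147 to 0.143 (5% cut) or 0.139 (10% cut).

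**Step 5: the other reading of 2.20 and 1.68.** SAP 3.8 does not say whether these are SDs of raw change. If they are, then with equal variances at baseline and Week 12 the baseline-adjusted SD is smaller by the factor √[(1 − r²)/(2(1 − r))]. That is 0.87, 0.89 or 0.92 for r = 0.5, 0.6 or 0.7. Power with the run-in diary alone is then 99.3% to 99.7% for micturitions and 99.0% to 99.5% for UUI, leaving less to gain in power. The proportional narrowing of the confidence interval is unaffected.

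**The case against.** Adjusting for the one defined baseline is a valid, unbiased choice; most trials could add a further prognostic covariate, and not doing so is no mistake. The trial already has 96% joint power on its own assumptions. The size of the gain comes from assumed correlations, and its floor is zero. The two diaries are not interchangeable: one follows washout and first training, the other is kept on placebo. OAB Type, Sex and Region may already carry part of the same information. All of this stands, and it is why the gain is put at 4% to 10% and the point is treated as an improvement only.

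A reader might infer three stronger things that the SAP does not support.
- **That the study is underpowered or the analysis wrong.** Step 1 shows the stated power is right.
- **That a demonstrated amount of precision is lost on both co-primaries and every diary endpoint.** UUI and volume voided were not modelled. The sensitivity and exploratory sections are largely blacked out, so the statement covers only the models shown.
- **That the gain could rescue the trial if the true effects were well below plan.** The SAP contains no such scenario, and the point does not rest on one.

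What the objection does not remove is that the data are already collected, the covariate cannot bias the contrast, and using it costs almost nothing.

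**Conclusion.** The point holds as a low-cost efficiency improvement. For micturitions the Week 12 residual variance would fall by about 0% to 17%, plausibly 4% to 10%. A 5% to 10% cut moves joint power from 96.0% to 96.9% to 97.7%, on the assumptions that UUI gains equally and that 2.20 and 1.68 are residual SDs. At the planning effects the practical benefit is slightly narrower confidence intervals and one to two points of joint power. The direction is secure unless the pre-Run-in diary predicts nothing beyond the run-in diary; the size rests on correlations the SAP does not give.

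**What to change.** Before unblinding, add one covariate, PREBASE, directly after BASE in the models of 8.1.1.1, 8.1.2.1, 8.2.2, 8.2.5 and 8.2.7, and in the matching subgroup models of 8.1.4. PREBASE is the patient's pre-Run-in diary average of the same variable, from at least 4 complete diary days; for volume voided it is the mean of that one day.

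The SAP should also:
- state the diary window for PREBASE, since 6.3 sets complete-day windows for Baseline and post-baseline diaries but none for the pre-Run-in diary;
- set a missing PREBASE to the mean over all arms, so that no patient leaves the FAS or FAS-I;
- leave the definitions of Baseline and change from baseline as they are;
- keep the model without PREBASE as a sensitivity analysis.

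The cost is one degree of freedom, a window rule, a missing-value rule and some SAP wording. It needs no new data and adds no patient burden.
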